Opioid Sparing Potential of Light-Induced Analgesia: a Pilot Trial of a Novel, Non-Pharmacological Treatment for Pain

Protocol 1.14 Approved November 10, 2020

Purpose of the study

This offers fascinating potential for use in opioid sparing multimodal analgesia while maintaining pain control, for which there is an urgent need. The green light effect is visually mediated. Further, the green-biased light spectrum involved can be obtained by filtering ambient light. Therefore, if such putative green light analgesia is possible in human populations, it would be inducible simply by using green lensed eyeglasses.

Our long-term goal is to test the efficacy of eyeglasses-based green light therapy as an analgesic adjunct. In particular, we aim to assess green light therapy's potential for broad adoption as an opioid sparing strategy while maintaining pain control. Reductions in opioid exposure are particularly important given links to opioid misuse risk. This aligns with national priorities aiming to identify interventions to prevent opioid misuse and abuse. The objective here, and the next step in pursuit of that goal, is to conduct a pilot trial testing clinical usage of green light therapy as an analgesic adjunct to opioid therapy. Our central hypothesis is that eyeglasses-based green light therapy will be well-tolerated and opioid sparing. The rationale for the proposed study is based on the published findings as described above. Namely, that green light visualization reduces pain responses. We expect that this effect will allow reduced opioid exposures in clinical care.

We will conduct the proposed pilot trial in both acute and chronic pain conditions. Patients scheduled for thoracic surgery with anticipated post-operative opioid treatment (acute surgical pain) and patients with fibromyalgia currently treated with opioids (chronic pain) will be identified, enrolled, and randomized to one of three arms: 1. clear eyeglasses (control), 2. green eyeglasses or 3. blue glasses

Design and Procedures

Trial Procedures – Acute Pain group:

Acute Pain group participants will be visited by study staff after their transfer to a floor unit (either normal care or step down; that is, after post-anesthesia care). Upon confirming their willingness participate, they will be randomized to receive either green, blue or clear glasses. Participants will be asked to wear their study glasses for at least 4 hours per day throughout their hospital stay and will be provided log books in which to record their glasses-wearing duration each day and any commentary they wish to share. During this visit, participants will also complete the PROMIS-57 Profile. The Patient-Reported Outcomes Measurement Information System (PROMIS) is a collection of patient-reported measures developed by an initiative of the National Institutes of Health as high-quality, well-validated, and standardized patient-reported outcomes measures across multiple domains. The PROMIS-57 Profile is a detailed, standardized battery of PROMIS measures covering anxiety, depression, fatigue, pain intensity, pain interference, physical function, sleep disturbance, and ability to participate in social roles and activities. On day of discharge or at 48 hours postoperative, whichever comes first, study

staff will again visit participants to collect the study glasses. Participants will again complete the PROMIS-57 Profile. During participants' inpatient stays, study staff will continue to coordinate with the primary care teams to monitor for any issues arising from the study or the use of the study glasses. Providers will be supplied with contact information to provide any feedback they wish to share.

For the postoperative patients in the study who are inpatient for the duration of the study, this is evaluated for them throughout their inpatient stay and the primary teams have the ability to address any sleep disturbance, mood change or change in the patients pain control per standard care. Should the providers caring for the patient or the patient themselves perceive the study intervention to be a significant contributor to the patients worsening condition, an adverse event will be recorded per the Data Safety Monitoring Plan and the patient will be withdrawn from the intervention/study.

Trial Procedures – Chronic Pain group:

Chronic Pain group participants will begin study procedures immediately following their enrollment. Participants will be randomized to receive either green, blue or clear glasses and will complete the PROMIS-57 Profile. Participants will be asked to wear their study glasses for at least 4 hours per day for a period of 2 weeks. Unlike the Acute Pain group in which pain will typically self-resolve with operative healing and the hospital stay provides a convenient and applicable treatment timeline, the appropriate duration of green light therapy for use in chronic pain states is unknown. Preclinical findings suggest the onset of analgesic effects after 3 days. However, such timelines rarely translate directly to human populations. Most pharmacological analgesics achieve effect onset within minutes to hours, although the analgesic effects of antidepressants upon chronic pain states (which may also involve modulation of descending pain control mechanisms) can require a week or longer to manifest. Here, we have chosen a moderate 2-week duration to allow for a range of times-to-onset. Participants will be provided log books in which to record their glasses-wearing duration, average pain, and opioid use each day. They will also be invited to include any commentary they wish to share.

For outpatients with fibromyalgia who are enrolled for 2 weeks all patients are administered the PROMIS-57 profile which evaluates the domains of sleep, mood and pain at enrollment, week 1 and at week 2 when the intervention ends. If there is any worsening of the patients condition in any of the domains, they will be offered immediate evaluation and management for the same. Should the providers caring for the patient or the patient themselves perceive the study intervention to be a significant contributor to the patients worsening condition, an adverse event will be recorded per the Data Safety Monitoring Plan and the patient will be withdrawn from the intervention/study.

All patients are provided with a phone number to call should they suffer from any side effects or worsening of their condition including any sleep disturbances.

Participants in this group will be asked to complete the PROMIS-57 Profile at the 1-week and 2-week time points. Two copies of the PROMIS-57 questionnaire will be given to the patient for completion at week 1 and week 2. A member of the study staff will call the patients at week 1 to

ensure completion of the questionnaire over the phone with the subjects. The week 2 questionnaire will be completed either over the phone (in the same way as week 1) or on site at the pain clinic. For patients completing the survey on site, the study staff will collect study materials (glasses and diary) at that visit. For patients completing the final study visit (week 2) over the phone, stamped and addressed shipping supplies will be provided to the patient for the return of the study materials (glasses and diary). Study staff will follow up with participants' pain providers to obtain any relevant feedback.

Selection of Subjects

Subjects will be identified through chart review using MaestroCare reports. Inclusion/exclusion criteria for the study will be:

Inclusion

- 1. Scheduled for thoracic surgery for which post-operative opioid PCA is anticipated (Acute Pain group) OR currently treated with opioid therapy for fibromyalgia (Chronic Pain group)
- 2. 18 years of age and older
- 3. Able to wear study eyeglasses for at least 4 hours per day

4. Agree to participate and provide written informed consent and HIPAA authorization Exclusion:

1. Color blindness (patients will be administered a color blindness test online at https://colormax.org/color-blind-test/

Recruitment and Compensation

In identifying and approaching all patients, the study team will coordinate with the primary clinical team. If the eligible patient agrees to hear more about the study, a study team member will attend, explain the study in detail, and obtain written informed consent. For patients who participate in remote enrollment, written electronic consent forms will be provided to the patient via email through REDCap and patients will sign and submit the e-consent. Study staff will then print a copy of the signed e-consent for our records and a copy will be automatically sent to the study participant as well. We will use the Duke hosted REDCap platform for collecting eConsent.

Study Interventions

Patients scheduled for thoracic surgery with anticipated post-operative opioid treatment (acute surgical pain) and patients with fibromyalgia currently treated with opioids (chronic pain) will be identified, enrolled, and randomized to one of three arms: 1. clear eyeglasses (control), 2. green eyeglasses or 3. blue eyeglasses.

Patients are able to withdraw from the study at any time as is clearly stated in the consent: "You can choose to stop participating at any time without penalty or loss of any benefits to which you are entitled. However, if you decide to stop participating in the study, we encourage you to talk to your doctor first."

For the postoperative patients (acute pain) who are inpatients for the time they are enrolled in the study, they continue to have access to opioid medications and other pain medications to address their pain per their primary teams per standard care.

For the outpatients (chronic pain) with fibromyalgia who are enrolled in the study, should they suffer from worsening pain may withdraw from the study at any time as is clearly stated in the consent: "You can choose to stop participating at any time without penalty or loss of any benefits to which you are entitled. However, if you decide to stop participating in the study, we encourage you to talk to your doctor first."

Participants are provided with a phone number to contact should they suffer from any side effects or worsening of their condition at which point the y would immediately be evaluated and managed to address their symptoms.

The patients will be managed for their pain per standard of care with the regimen decided by their treating physician. The only intervention based on the study will be the introduction of the glasses which participants are required to wear for 4 hours during the day. There is NO change made to the patients pain management regimen, it is as per their primary treating physician.

This is not standardized in the 3 groups as we will be recording the medications used for pain and their utilization.

Patients will be exposed to ambient light, no standardized source of light. We will ask patients to document their 4 hours of usage of the glasses during each day for exact times worn and whether they were indoors or outdoors. In this pilot study we hope to understand patient usage patterns and compliance factors to inform a larger study in the future.

The eyeglasses which will be used for this study are commercially obtained from online vendors. They are then tested to ensure they meet the below requirements

Eyeglasses

Thanks to recent fashion trends and the dramatic expansion of e-commerce enabling low-cost niche manufacturing, a wide array of eyeglasses in varying styles and colors are now easily available. To identify eyeglasses for use in this trial, we purchased several different examples from a major online retailer. We screened these eyeglasses for perceived lens color (as some eyeglasses relied on reflective coating to appear green, but did not transmit perceptibly green light), fit (across various study personnel and colleagues), subjective build quality, aesthetic acceptability, and availability of matching clear-lensed versions for use as controls. The remaining eyeglasses were subjected to transmission spectroscopy across the 425nm to 700nm

visual spectrum. On the basis of these spectra, the eyeglasses with the most green-biased transmission will be chosen for use in this study.

The brand we have tested with spectroscopy which meet the above requirements (shown on mannequin below) are WearMe Pro - Colorful One Piece Transparent Round Super Retro Sunglasses: Green. The blue glasses were selected from the same manufacturer: WearMe Pro - Colorful One Piece Transparent Round Super Retro Sunglasses: Blue. These specific glasses have been chosen as they are registered with the FDA as a medical device; registration of these glasses can be found on the FDA website (fda.gov) under registered medical devices. (Full spectroscopy analysis for the glasses has been attached).

Data Analysis and Statistical Considerations

We calculate that a total enrollment of 120 participants will be sufficient to provide greater than 95% confidence in detecting issues with a 5% probability of occurrence. Divided evenly across Acute Pain and Chronic Pain groups (60 each) this sample will also provide approximately 80% confidence in detecting issues with a 5% probability of occurrence in only one group. This yields a 15 participant per condition (acute/chronic x green/clear/blue) sample size. Adding the blue glasses group to compare, continues to allow us a similar confidence in detecting issues with a 5% probability of occurrence in detecting issues with a 5% probability of occurrence in detecting issues with a 5% probability of occurrence in detecting issues with a 5% probability of occurrence in detecting issues with a 5% probability of occurrence in detecting issues with a 5% probability of occurrence in detecting issues with a 5% probability of occurrence in detecting issues with a 5% probability of occurrence in detecting issues with a 5% probability of occurrence in detecting issues with a 5% probability of occurrence in detecting issues with a 5% probability of occurrence in detecting issues with a 5% probability of occurrence in detecting issues with a 5% probability of occurrence in one group.

Interestingly, this chosen sample size also fulfills several other methods/guidelines for pilot trial sample sizes which range from 10 to 15 per condition. These methods have generally sought to power pilot trials to produce usable estimates of outcome measure values. While the appropriateness of such an approach is debated, it does suggest that our chosen sample size will be satisfactory to produce such estimates.

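### The acute group has a baseline and only one on-treatment pain assessment, so its opioid use cannot be set against pain over the same period

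*Combined protocol and SAP*

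**What the plan says.** Under Trial Procedures – Acute Pain group, patients are randomized on the floor unit after post-anesthesia care and given "log books in which to record their glasses-wearing duration each day and any commentary they wish to share". The first pain measurement is at that visit: "During this visit, participants will also complete the PROMIS-57 Profile". The instrument is described as "covering anxiety, depression, fatigue, pain intensity, pain interference, physical function, sleep disturbance" and social participation. The closing visit is set as follows: "On day of discharge or at 48 hours postoperative, whichever comes first, study" staff return for the glasses, and "Participants will again complete the PROMIS-57 Profile". The same section says that primary teams evaluate and manage pain control under standard care during the stay. It does not describe this as a study data item.

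Under Trial Procedures – Chronic Pain group, patients receive "log books in which to record their glasses-wearing duration, average pain, and opioid use each day", and the PROMIS-57 is given "at enrollment, week 1 and at week 2 when the intervention ends".

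Study Interventions says that analgesic regimens are left to the treating physician and not standardized across arms, and that pain medications and their use are recorded. It also asks patients to note the times the glasses were worn and whether they were indoors or outdoors. It mentions no pain scores.

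Purpose of the study puts the pain-control condition under the long-term goal, as "potential for broad adoption as an opioid sparing strategy while maintaining pain control". The pilot's central hypothesis names tolerability and opioid reduction only.

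**The concern.** In the acute group, opioid use depends on pain and also changes it. Patients are selected because a postoperative opioid PCA is expected, they keep access to opioids and other analgesics, and regimens differ by physician. A lower opioid total in one arm could mean less pain, the same pain treated differently, or more pain tolerated. Pain measured over the hours in which the opioid was used helps to separate these readings.

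A single closing assessment does this poorly. The protocol itself notes, in the chronic section, that acute pain usually resolves with healing, so arms that differed earlier could look alike at the end. The closing assessment also falls at different times for different patients, because it is tied to the earlier of two events. The protocol explains why the two groups have different treatment durations, but not why the daily pain item appears in one log and not the other.

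**Working it through.** **Reproducing a figure.** The plan gives no number on this point, so there is none to reproduce. The check is a count of scheduled pain assessments, followed by the likely gain from the fix.

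**Count, from the two Trial Procedures sections.**

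| | Acute | Chronic |
|---|---|---|
| Baseline PROMIS-57 | 1 (visit where glasses are assigned) | 1 (enrollment) |
| On-treatment PROMIS-57 | 1 (discharge or 48 hours) | 2 (weeks 1 and 2) |
| Daily pain item in the log | 0 | about 14 (2 weeks × 7 days) |
| Opioid use | recorded as pain medication use (Study Interventions) | recorded daily in the log |

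The acute group therefore has a before-and-after pain measure and nothing scheduled in between.

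**Entries a daily item would add.** Glasses are given after post-anesthesia care and collected no later than 48 hours after surgery. Wear therefore lasts less than 48 hours, which gives about k = 2 daily entries.

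**Precision of their mean.** The variance of a mean of k equally correlated ratings, relative to one rating, is (1 + (k − 1)ρ)/k. The documents give no ρ; 0.4 to 0.8 is an assumed range. With k = 2:

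- ρ = 0.4: (1 + 0.4)/2 = 0.70
- ρ = 0.6: (1 + 0.6)/2 = 0.80
- ρ = 0.8: (1 + 0.8)/2 = 0.90

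The reciprocals are 1/0.70 = 1.43, 1/0.80 = 1.25 and 1/0.90 = 1.11. The gain in precision is thus equivalent to 11% to 43% more patients for a pain comparison, and 25% at ρ = 0.6.

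**Sensitivity to k.** Three entries at ρ = 0.6 would give (1 + 1.2)/3 = 0.73, and 1/0.733 = 1.36. A window of under 48 hours does not reliably supply three daily entries, so this figure should not be relied on.

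These ratios describe the precision of a mean. They do not measure the main problem, which is that the interval between the two visits is not covered.

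**The case against.** The strongest reply is that the acute group is measured twice with an instrument that includes pain intensity and pain interference, so closing pain and its change can be compared between arms. This is correct. A reader might infer from the log that the acute group has no repeated study pain measure; the PROMIS-57 schedule shows otherwise.

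The exposure is also short. The last daily entry would largely coincide with the closing PROMIS-57, and a 14-day outpatient log is not a close comparator. This stands, and it limits the gain.

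The difference between the logs may also be deliberate. Outpatients have to report their own pain and opioid use, whereas inpatients are observed by staff. The acute log omits opioid use too, yet medication use is recorded elsewhere, so absence from the log does not prove absence from the data. That is a fair caution. But for medication the protocol says that the data are recorded; for inpatient pain scores it says nothing of the kind.

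Finally, a reader might infer that lower opioid use bought with more pain would be declared a success, or that a powered pain comparison is being weakened. The documents support neither. They contain no success rule, and Data Analysis and Statistical Considerations sizes the trial on detecting issues with a 5% probability of occurrence. Pain control is part of the long-term goal, not of the central hypothesis. The study also withholds no analgesic, so pain persisting to the end could show on the closing PROMIS-57.

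**Conclusion.** The point holds as a modest, inexpensive improvement and not as a flaw that undermines the pilot. The acute group has one baseline and one on-treatment study pain assessment, no daily pain record, and no stated plan to capture inpatient pain scores. A difference in opioid use could be set against pain at the end of treatment, but not against pain over the period of use. The pilot is described as a step toward the long-term goal, and that goal needs the second comparison.

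The size is about two further ratings per patient, with the mean having 0.70 to 0.90 of the variance of a single rating (0.80 at a correlation of 0.6). This assumes equal correlation between ratings in the range 0.4 to 0.8, about two completed entries, and medication recording that covers the whole time the glasses are worn; the protocol gives no window for the last. It also treats the closing PROMIS-57 as a single assessment, since the documents do not state the recall period of its pain items. The conclusion that pain between the visits is not scheduled for study measurement rests on the text alone and does not depend on the correlations.

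**What to change.** In Trial Procedures – Acute Pain group, add the chronic log's daily average-pain item to the acute log, from receipt of the glasses to their collection. Alternatively, state that inpatient pain scores recorded over that window will be extracted as study data, and name the scale and the summary to be used.

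In Data Analysis and Statistical Considerations, state that the acute difference between arms in opioid use will be reported beside the difference in mean pain, both over the same window and with confidence intervals. Present this as estimation, without a claim of power.

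The log option costs one line in an existing form and a minor burden on patients for up to about two days, with no extra visit or procedure. Extraction spares the patients but takes staff time, and works only if usable scores are recorded routinely, which the protocol does not say. Neither option alters treatment. The choice should be made before enrollment, because patients cannot reliably supply these ratings afterwards.

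### Chronic-group diary lists opioids as its only medication, although the protocol relies on recording all pain medications to justify regimens that are not standardized

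*Combined protocol and SAP*

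**What the plan says.** Three parts of the combined protocol and SAP bear on this.

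- **Purpose of the study** sets the hypothesis: "Our central hypothesis is that eyeglasses-based green light therapy will be well-tolerated and opioid sparing". The same section places opioid sparing within multimodal analgesia, with pain control maintained.
- **Study Interventions** leaves background analgesia to routine care: "The patients will be managed for their pain per standard of care with the regimen decided by their treating physician". It adds: "There is NO change made to the patients pain management regimen, it is as per their primary treating physician". It then explains why differing regimens are acceptable: "This is not standardized in the 3 groups as we will be recording the medications used for pain and their utilization". That sentence is limited neither to opioids nor to one pain group. It gives no source, form or timing for the record.
- **Trial Procedures – Chronic Pain group** describes the outpatient diary for the 2-week period: "Participants will be provided log books in which to record their glasses-wearing duration, average pain, and opioid use each day". Free text is optional: "They will also be invited to include any commentary they wish to share".

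**The concern.** Recording all pain medications is the stated reason for not standardizing regimens. In the chronic group, the one described instrument that captures daily intake at home asks about opioids and no other drug. Staff who build the diary from its own description would leave non-opioid analgesics out, and the commitment under Study Interventions would have no instrument behind it.

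At stake is the interpretation of opioid use and of daily average pain. Suppose the green arm ends with a lower opioid total and unchanged pain. The glasses may have helped, or participants may have taken more of another analgesic. With both kinds of intake recorded, the reader can look. With opioids alone, the reader cannot, and as-needed or over-the-counter use that was never written down during the 2 weeks cannot be reliably recovered by a later analysis.

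**Working it through.** The plan gives no figure on this point to reproduce. The main check is to compare the commitment with each source the protocol describes for chronic outpatients.

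| Possible source | What the protocol says it collects | Non-opioid intake at home? |
|---|---|---|
| Daily diary (Chronic Pain group procedures) | Wear time, average pain, opioid use | Not listed |
| Diary commentary (same section) | Whatever the participant chooses to write | Only if volunteered |
| Wear-time detail (Study Interventions) | Times worn, and indoors or outdoors | No |
| Week 1 call and week 2 call or visit | PROMIS-57; return of glasses and diary | Not mentioned |
| PROMIS-57 (domains listed in the Acute Pain group procedures) | Anxiety, depression, fatigue, pain intensity and interference, physical function, sleep, social roles | No medication domain |
| Pain-provider contact | "Study staff will follow up with participants' pain providers to obtain any relevant feedback" | No medication data specified |
| Chart review (Selection of Subjects) | Identification of eligible patients | Not stated as an outcome source |

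No row supplies the record that Study Interventions promises for non-opioid drugs. Data Analysis and Statistical Considerations defines no analysis of opioid use and no handling of non-opioid analgesics, so the gap is not closed there either.

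**Illustration of chance imbalance.** Randomization balances co-analgesic use on average, but the arms are small.

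- Arm size n: the protocol states 15 per condition. It also states 60 per pain group, and 60/3 = 20 per arm. The two do not agree, which is a separate matter, so both are shown.
- Rate p of using or changing a non-opioid analgesic: not in the documents. Assumed 20%, 30% and 50%, equal in both arms.
- Cutoff: a green-clear difference of 20 percentage points or more, chosen for illustration. This is 0.20 × 15 = 3 participants, or 0.20 × 20 = 4.

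With X and Y independent Binomial(n, p), the probability is P(|X − Y| ≥ 0.20n), summed exactly over all pairs (x, y):

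| p (assumed) | n = 15 per arm | n = 20 per arm |
|---|---|---|
| 20% | 0.249 | 0.164 |
| 30% | 0.318 | 0.226 |
| 50% | 0.362 | 0.268 |

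These are probabilities of an imbalance in co-analgesic use in either direction. They are not estimates of bias in opioid use, and such imbalances would occur whether or not they were logged. They show only that a visible difference between arms would be common at this size, and that a diary without non-opioid items could not describe it.

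**The case against.** The strongest reply is that nothing here contradicts. Study Interventions commits to recording pain medications, and the diary description never says that its list is complete. The list is in fact incomplete, because Study Interventions also asks patients to note when the glasses were worn and in which setting. The calls, the clinic contact and the provider follow-up could each carry a medication question. This stands in part: the documents show an unspecified source, not proof that the data will be missing. But for the wear-time detail the protocol says that patients will document it, while for pain medications it names nobody and no form.

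Three stronger readings are tempting and are not supported.

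- **That the green-clear contrast could not be interpreted.** Arms are randomized, so opioid use under usual care remains a valid comparison. A systematic difference in substitution would be a consequence of assignment, and a chance difference is ordinary sampling error. Co-analgesic data help to explain a result; they are not needed to make the comparison valid.
- **That the problem belongs to the chronic group alone.** The acute-group log lists wear time and commentary and no medication at all, and no section names a medication source for inpatients. Assuming that hospital records fill that gap relies on something the protocol does not say. The point is made for the chronic group because that is where the protocol describes a medication diary and limits its listed drugs to opioids.
- **That the gap can be expressed as lost effect or extra sample size.** This would need opioid and non-opioid intake on one additive scale, with total analgesic intake as the target. The documents support neither, and the stated hypothesis concerns opioids.

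It is also fair to say that this is a pilot sized mainly on detecting issues, with no defined opioid endpoint, so a diary item alone would not settle attribution. That limits the weight of the point but does not remove it: Study Interventions says the pilot is meant to inform a larger study, and an item left out of the diary cannot be added afterwards.

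**Conclusion.** The point holds as a gap in specified data capture. The protocol relies on recording pain medications and their use, yet for chronic outpatients the only described record of home intake lists opioids as its sole medication. If the diary follows that list, as-needed and over-the-counter non-opioid use may go unrecorded, and a lower opioid total with steady pain becomes harder to attribute to the glasses.

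The size cannot be fixed from the documents. The imbalance probabilities (25% to 36% at 15 per arm, 16% to 27% at 20) rest on assumed rates of use and an arbitrary 20-point cutoff, and the conclusion does not depend on them. It rests on two readings of the text: that the commitment covers non-opioid drugs, because it speaks of pain medications without restriction, and that no other section names a source for them. This is an inexpensive improvement to data collection, not a flaw that invalidates the trial.

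**What to change.** Reconcile the two sections by changing the diary content under Trial Procedures – Chronic Pain group. Suggested text: glasses-wearing duration, average pain, and all medications taken for pain (opioid and non-opioid, including over the counter; name, dose, number taken) each day.

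Under Data Analysis and Statistical Considerations, add a descriptive table for the chronic group showing non-opioid analgesic use by arm beside opioid use. No test is needed, and nothing in any patient's treatment changes.

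The cost is one more block on the existing diary, one table, and slightly more diary burden for chronic participants. No added visits, staff or patients are required.
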